## FLOWCHARTS

| Period                             | Screening | Intervention |
|------------------------------------|-----------|--------------|
|                                    | (-t1)     | (t1)         |
| Enlistment                         |           |              |
| informed consent                   | -         |              |
| inclusion/exclusion criteria       | -         |              |
| Administration of the intervention |           |              |
| Biological sample collection       |           | -            |

## LIST OF ABBREVIATIONS

ADH: alcohol dehydrogenase ARAT:

retinol acyltransferase GWAS: genome-

wide association study HSCs: Hepatic

stellate cells

LRAT: lecithin retinol acyl-transferase

MMP13: matrix metalloprotease 13

NAFLD: nonalcoholic fatty liver disease

NASH: nonalcoholic steatohepatitis

PNPLA3: Patatin-like phospholipase domain-containing protein 3

RA: retinoic acid

RALDH: retinaldehydedehydrogenase-- TGF $\beta$ 1:

transforming growth factor  $\beta$ 1 TIMP: tissue

inhibitor matrix metalloproteases

-SMA:  $\alpha$ -smooth muscle actin

## 1. INTRODUCTION

### 1.1 Background and rationale

Nonalcoholic fatty liver disease (NAFLD), defined as the accumulation of fat in the liver not explained by risky alcohol consumption, is the leading cause of liver damage and occurs in approximately one-third of the population (25–30%). NAFLD encompasses a broad spectrum of conditions ranging from simple steatosis to nonalcoholic steatohepatitis (NASH). NASH is defined histologically by the coexistence of steatosis, lobular inflammation, and hepatocellular damage and is frequently complicated by the development of fibrosis. NASH occurs in 20–30% of patients with NAFLD and may progress to cirrhosis and hepatocellular carcinoma (HCC) (1). Recent advances in genetics have highlighted that genetic factors play a key role in the susceptibility, severity, and long-term prognosis of the disease (2). In particular, in a genome-wide association study (GWAS) conducted on a multiethnic population, the gene was identified PNPLA3 (Patatin-like phospholipase domain-containing protein 3), located on chromosome 22, as the major genetic factor that strongly associates with intrahepatic fat content, independently of body mass and insulin resistance (3). In particular, the polymorphism in the gene PNPLA3 (rs738409, C>G), which determines an amino acid substitution from isoleucine to methionine in position 148 of the protein (I148M), currently represents the most important genetic predictor of steatosis, steatohepatitis and progression of liver damage and strongly increases the risk of developing hepatocellular carcinoma (4, 5). PNPLA3 encodes a protein, also called adiponutrin, located at the level of the endoplasmic reticulum and on the surface of lipid droplets, with an important enzymatic function (triacylglycerol lipase), involved in the hydrolysis of triglycerides in hepatocytes and adipocytes and in the catabolism of retinol esters in stellate cells. The presence of the amino acid methionine in position 148 would lead to a loss of function of the protein with accumulation at the surface of lipid droplets and reduced remodeling of triglycerides (6). Furthermore, it has been demonstrated that PNPLA3, following induction by TGF-, regulates the metabolism of retinol in stellate cells (retinyl-esterase activity) determining the release of retinol ex vivo and in vitro (7). The risk variant 148M instead seems to prevent the release of retinol. Furthermore, it has been observed that the progression of chronic liver diseases related to steatosis is associated with cellular senescence and therefore patients carrying the risk variant (148M) show an up-regulation of cellular senescence and pathways fibrogenic.

These preclinical studies suggest PNPLA3 as a new therapeutic target, especially with regard to the possibility of reducing its expression in the mutated variant. Therefore, screening based on the determination of the I148M variant status of PNPLA3 could be fundamental for designing future precision medicine approaches. Although the I148M variant of PNPLA3 causes progression of liver damage to advanced fibrosis and hepatocellular carcinoma (1), the phenotypic expression is highly variable and depends on the coexistence of other genetic factors and environmental factors. Furthermore, the relative contribution of the I148M variant carrier state on the steatohepatitis phenotype in

hepatocytes vs. stellate cells is not yet clear. The study of new molecular pharmacological approaches that aim at regulating the expression and activity of PNPLA3 for the prevention and treatment of liver diseases is however still difficult, due to both the limitations of experimental models in animals (cost, suffering, different regulation of lipid metabolism and PNPLA3 compared to humans) and the difficulty of reproducing NASH in models *in vitro*.

The current models *in vitro*, based on liver cell lines, are in fact unable to reproduce the intrinsic cellular heterogeneity, the three-dimensional architecture of the tissue and the cell-cell interactions. These characteristics are fundamental in the study of the processes that can lead to the onset of steatosis, progressing to a fibrotic, cirrhotic and tumorous state following an external insult.

Organoids, three-dimensional (3D) cellular structures, generated both from induced pluripotent stem cells and from tissue-resident adult stem cells, are recently establishing themselves as a new culture model to overcome the limitations of traditional cell culture systems, emerging as powerful tools for the study of human diseases (8, 9). This is possible because they are able to stably preserve the genetic information of the autologous tissue and mimic the physiological and pathological state of the tissue of interest. Despite the cellular heterogeneity exhibited by organoids, these structures present some limitations such as the low capacity to mimic the architecture of the mature organ of interest due to the absence of cells that compose the surrounding environment (10, 11). This limitation can be overcome by creating 3D cultures, defined as "assembloids", composed of the cells that constitute the organoids in co-culture with cells of the surrounding environment (stromal, stellate, endothelial cells, etc.), capable of recreating a more precise architecture of the starting tissue, represented by the epithelial component surrounded by its stroma (12, 13). These structures will be the basis for studying the molecular mechanisms that underlie the onset of steatosis and its progression to a fibrotic condition, due to the activation of stellate cells, following the damage suffered by hepatocytes.

## 2. OBJECTIVE OF THE EXPERIMENT

The aim of this project is to study the cellular and molecular mechanisms through which the variant at risk of PNPLA3 (148M) accelerates the progression of liver damage in models based on the development of liver organoids and assembloids, and to test in these the efficacy of new molecular pharmacological approaches aimed at silencing the expression of the mutated protein variant in improving the pathological phenotype. Our hypothesis is that the loss of function of PNPLA3 in hepatocytes and hepatic stellate cells may represent a link between accumulation of hepatic fat, development of lipotoxicity and inflammation, fibrosis and finally liver cancer. The 148M variant could determine a persistent and uncontrolled activation of stellate cells (HSCs) due to an altered ability to release retinol. Activated HSCs would then undergo premature senescence with consequent release of pro-inflammatory and carcinogenic mediators. Silencing of PNPLA3 by using antisense RNA would therefore lead to a greater improvement of the

hepatocellular damage specifically in models derived from cells carrying the risk variant.

## 2.1 Primary objective

The primary objective of the study conducted at the Foundation is to generate and characterize three-dimensional models, called “assembloids”, composed of the main liver cell populations (in particular from the coculture of organoids derived from clinical samples together with stellate cells responsible for fibrogenesis). These models will be used to mimic the early stages of steatohepatitis onset in conditions of altered lipid metabolism (induced by exposure to the main environmental determinants of this condition: excess fatty acids, fructose, cholesterol) in the presence or absence of the I148M mutation of PNPLA3. Other genetic variants will also be evaluated.

## 2.2 Secondary objectives

1. Identification of novel non-invasive biomarkers of pathological activation of human stellate cells and progression of liver damage to be subsequently validated in clinical series for future use in clinical management for individual risk stratification.
2. Study of epigenetic factors underlying the onset of non-alcoholic steatohepatitis and its progression to fibrosis, cirrhosis and HCC.
3. Evaluation of the impact of antisense oligonucleotides directed against PNPLA3 on the severity of the “steatohepatitic” phenotype (lipid accumulation, lipotoxicity and inflammation and fibrogenesis) in assembloids.

## 3. STUDY DESIGN

### 3.1 Study design

Genetic interventional, with the collection of biological, non-pharmacological, monocentric material.

## 3.2 Inclusion criteria

Patients of legal age who have given consent to participate in the study will be included and will be listed for the following procedures:

- liver biopsy for suspected nonalcoholic steatohepatitis (NASH) at the time of diagnosis;
- liver resection for hepatocellular carcinoma or other liver lesions (including secondary lesions from other neoplasms and benign focal lesions, which will allow obtaining starting liver tissue

healthy);

- post-transplant healthy liver biopsies;
- cholecystectomies.

You will also be required:

- willingness to sign informed consent for the study
- availability of DNA sample for genetic analysis and clinical data,
- blood sampling for genetic and epigenetic analysis and analysis of non-coding RNAs (lncRNAs, miRNAs and circRNAs).

### 3.3 Exclusion criteria

Patients with the following will be excluded:

- positivity for chronic viral hepatitis (HCV-RNA and/or HBsAg);
- positivity to other liver diseases such as autoimmune and viral hepatitis (hepatitis B and C), hereditary hemochromatosis, alpha-1-antitrypsin deficiency, Wilson's disease.

## 4. PROCEDURES RELATING TO THE STUDY

### 4.1 Intervention

In collaboration with the Liver Transplant Unit of the Foundation, samples of discarded tissue from patients undergoing liver resection will be collected (both intra-tumoral and extra-tumoral tissues in the case of hepatocarcinoma) or taken from the whole liver post-transplant. This procedure will not entail any additional risk for the patient compared to the usual routine, nor will it reduce the availability of material for standard pathological analyses.

These samples will allow us to isolate cells (ovalocytes – liver progenitor cells) to generate organoids from normal liver tissue (cholecystectomy) and suspected NASH.

We plan to collect up to 20 independent samples per tissue type. The groups considered will be:

- organoids, cultures of sinusoidal stellate cells isolated from 20 patients with CC genotype (I148I)
- organoids, cultures of sinusoidal stellate cells isolated from 20 patients with CG genotype (I148M)
- organoids, cultures of sinusoidal stellate cells isolated from 20 patients with GG genotype

(M148M)

A blood sample (approximately 7 cc) will also be taken, in addition to those already scheduled during regular clinical checks, at the time of surgery or liver biopsy.

It is planned to share a portion of the liver biopsy samples for immunohistochemical analysis to be carried out at the Division of Medicine, Institute for Liver and Digestive Health, University College London, in collaboration with [name], in order to further evaluate the expression of PNPLA3 associated with liver disease, subject to the preparation of an appropriate MTA.

#### 4.2 Isolation and culture of organoids

Biopsy fragments or fragments obtained from surgical resections will be transported in Celsior perfusion solution at 4°C and will be processed at the Translational Medicine laboratory, UOC Transfusion Center of the Foundation within 24 hours of collection to isolate liver organoids. The tissues will be mechanically fragmented into small pieces avoiding reducing them to single cells; this will increase the efficiency of organoid formation. Then the fragments will be further subjected to enzymatic digestion with a solution containing Collagenase and DNase at 37°C. The cell clusters obtained from enzymatic digestion will be included in reduced growth factor Matrigel. Once the Matrigel has polymerized, the complete culture medium for liver organoids will be added: Advanced DMEM/F12 supplemented with 1% N2 and 1% B27 (both from GIBCO), 1.25 mM N-Acetylcysteine (Sigma), 10 nM Leu-Gastrin (Sigma), 50 ng/ml EGF (Peprotech), 1 -g/ml RSPO1 (Peprotech), 100 ng/ml FGF10 (Peprotech), 25 ng/ml HGF (Peprotech), 10 mM Nicotinamide (Sigma), 5 -M A83.01 (Peprotech) and 10 -M Forskolin (Peprotech). In order to increase the efficiency of organoid isolation, 25 ng/ml Noggin (Peprotech), 100 ng/ml Wnt3a (peprotech) and 10 -M Rock inhibitor Y27632 (Peprotech) will be added to the medium for the first few days. The organoids will then be differentiated towards a hepatocyte phenotype.

#### 4.3 Isolation and culture of sinusoidal stellate cells

A part of the biopsy fragments or those obtained from surgical resections, once digested to obtain the epithelial cells that will form the organoids, will be processed to obtain hepatic stellate cells (HSC) and sinusoidal cells (LSEC). The latter will be isolated by exploiting their low density, due to the presence of lipid droplets that characterize them. The stellate cells will be cultured on plastic and we will characterize their activation state and the purity of the cell population, by flow cytometry and quantitative Real Time PCR (RT-qPCR), evaluating the presence of the

retinol and specific cellular markers (15). Sinusoidal cells will be cultured on plastic pre-treated with a fibronectin coating and grown in the presence of the growth factor VEGF.

#### 4.4 Generation of assemblyloids

In order to obtain the assemblyloids, both the organoids and the stellate and sinusoidal cells will be dissociated into single cells by enzymatic digestion using trypsin. The cells will then be included in reduced growth factor Matrigel in different ratios in order to mimic the physiological conditions present in the liver tissue. Once the Matrigel has polymerized, the culture medium appropriately formulated to allow the survival of both hepatocytes, ductal cells and stellate cells will be added: Advanced DMEM/F12 supplemented with 1% N2 and 1% B27 (both from GIBCO), 1.25 mM N-Acetylcysteine (Sigma), 10 nM Leu-Gastrin (Sigma), 50 ng/ml EGF (Peprotech), 25 ng/ml HGF (Peprotech) and 2% FBS (GIBCO).

#### 4.5 Treatment in vitro

It has recently been shown that the addition of oleate and palmitate to the culture medium is able to increase the formation of lipid droplets in hepatocytes and primary stellate cells, simultaneously causing a down-regulation of the expression of PNPLA3. Conversely, in the absence of retinol and palmitate, a reduction in intracellular lipid content and an increase in the expression of PNPLA3 (7).

The generated assemblyloids will be treated for 36 or 120 hours with oleic acid and palmitic acid (300  $\mu$ M both) (Sigma Aldrich, St Louis, MO). Treatments with the addition of cholesterol, fructose, insulin and low concentrations of ethyl alcohol will also be tested to mimic a condition of dysmetabolism, unbalanced diet and the main environmental determinants of liver disease. This experiment will allow us to evaluate differences in the accumulation and subsequent release of lipid droplets in cells with different genotypes of PNPLA3. After 36 hours, the lipid droplet content will be visualized by OilRed O histochemical staining. An analysis of stellate cell activation will also be performed after 36 hours. Instead, after 120 hours, the assemblyloids will be partly fixed in formaldehyde to analyze morphology, biomarkers and fibrotic status and partly frozen in liquid nitrogen for further gene expression analysis.

PNPLA3 will be silenced using antisense RNA (16)

#### 4.6 Genetic Analysis

DNA will be extracted by phenol-chloroform from peripheral blood and the I148M variant

PNPLA3(rs738409) will be determined by TaqMan assay on ABI 7500 Fast apparatus (Life Technologies, Carlsbad, CA, USA) (17).

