## 5. ENDPOINTS

### 5.1 Primary Endpoints

1. Isolation of epithelial cells in order to generate models of the main populations of liver cells in a three-dimensional culture environment, called organoids, and molecular characterization of the generated models. Isolation of stellate cells and their phenotypic and molecular characterization. Generation of assemblyloids that mimic the hepatic tissue architecture and its phenotypic and molecular characterization to study the onset and development of steatohepatitis.
2. Evaluation of the impact of the I148M variant (evaluation of possible combinations both in epithelial cells - hepatocytes and in stellate cells) on the steatohepatitic phenotype in human liver assembloids, with particular reference to:
  - Lipid accumulation in hepatocytes (quantitative and qualitative analysis)
  - Lipotoxicity and expression of inflammatory markers (gene expression)
  - Activation of fibrogenesis (assessment of the activation state of stellate cells, retinol metabolism and extracellular matrix deposition)

Steatohepatitis will be defined in the simultaneous presence of all these alterations in the assemblage.

3. Analysis of variants of the TM6SF2, MBOAT7 and GCKR genes, previously correlated with the development of non-alcoholic steatohepatitis (14).

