### Secondary Endpoints

- Knowledge of the behavioral and morphological differences between physiological and NASH hepatocytes and stellate cells.
  - Detection of new biomarkers predictive of the development and progression of the disease.
- a. - Analysis of epigenetic differences in physiological conditions, onset and progression of NASH.

- Knowledge of the molecular mechanisms underlying cellular-level observations using "omics" scale assessments and CRISPR-Cas9 genetic engineering.
- Analysis of the impact of PNPLA3 silencing on the steatohepatitis phenotype of human liver assembloids, stratified by I148M variant carrier status in epithelial cells vs. stellate cells.

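### Cultures from post-transplant graft biopsies would be grouped by the recipient's PNPLA3 genotype, not by that of the cultured cells

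*Protocol*

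**What the plan says.** Section 4.6 gives the genotyping method: "DNA will be extracted by phenol-chloroform from peripheral blood and the I148M variant" (rs738409) is then determined by TaqMan assay. No other DNA source is named. Section 3.2 asks for "blood sampling for genetic and epigenetic analysis", and section 4.1 takes about 7 cc from the participant "at the time of surgery or liver biopsy". It also groups cultures by the genotype of the patients they were isolated from: 20 CC, 20 CG and 20 GG.

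Among the eligible procedures in section 3.2 are "post-transplant healthy liver biopsies". Sections 4.2 and 4.3 culture biopsy fragments into organoids and stellate cells. Section 10.2.3 requires consent from the recipient of the transplanted organ, so the recipient is the participant. Section 4.1 also mentions tissue "taken from the whole liver post-transplant", without saying whether this is the graft or the recipient's own removed liver.

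**The concern.** A healthy biopsy taken after transplantation comes from the graft. Its epithelial and stellate cells carry the organ donor's inherited genotype, while the blood drawn at that biopsy carries the recipient's. Under section 4.6 such a culture would join the CC, CG or GG group on a genotype it need not have.

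The genotype of the cultured cells is the exposure in primary endpoint 2. Labels unrelated to the true genotype dilute the GG vs CC contrast towards zero. The blood result alone cannot reveal the error.

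The same label feeds the secondary silencing analysis, "stratified by I148M variant carrier status in epithelial cells vs. stellate cells". If the other genes are typed from the same blood, it also affects primary endpoint 3, "Analysis of variants of the TM6SF2, MBOAT7 and GCKR genes".

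Resections, biopsies for suspected NASH and cholecystectomies are not affected, because they yield the patient's own tissue.

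**Working it through.** **Inputs from the protocol (section 7.1).** Steatohepatitis phenotype in 75% (GG) vs 25% (CC), 20 vs 20, two-sided alpha 0.05, stated power 95%, chi-square test.

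**Assumptions not in the protocol.** Organ donor and recipient are unrelated. Genotypes follow Hardy-Weinberg proportions with risk-allele frequency q, and p = 1 − q. The CG phenotype rate is c. A share f of the cultures in a labelled group is graft-derived. Ranges used: q from 0.106 to 0.5 (0.106 corresponds to 20% carriers) and c from 25% to 75%.

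**Step 1: the stated power.** With unpooled variance:
- SE = √(2 × 0.75 × 0.25 / 20) = 0.137
- power = Φ(0.50/0.137 − 1.96) = 95.5%, which reproduces the stated 95%

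Exact enumeration of the uncorrected chi-square test gives 90.1%. Both are carried forward as baselines.

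**Step 2: how often the label is wrong for a graft culture.** The donor's genotype is independent of the recipient's, so the chance of a wrong label is 1 − p² (CC), 1 − 2pq (CG) and 1 − q² (GG).

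| q | labelled CC | labelled CG | labelled GG |
|---|---|---|---|
| 0.106 | 20% | 81% | 99% |
| 0.2 | 36% | 68% | 96% |
| 0.5 | 75% | 50% | 75% |

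The three chances sum to 3 − (p² + 2pq + q²) = 2. If graft cultures are spread evenly over the three equal groups, two-thirds are therefore mislabelled whatever q is.

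**Step 3: effect on the contrast.** A graft culture shows the phenotype with probability m = 0.25p² + 2pqc + 0.75q², whatever its label. Then
- labelled GG: (1 − f) × 0.75 + f × m
- labelled CC: (1 − f) × 0.25 + f × m
- difference: (1 − f) × 0.50, because m cancels

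Example with q = 0.3, c = 0.5, f = 0.10: m = 0.1225 + 0.21 + 0.0675 = 0.40. The rates are 0.715 and 0.265, a difference of 45 points. The unpooled SE is √((0.715 × 0.285 + 0.265 × 0.735)/20) = 0.141, so power is Φ(0.45/0.141 − 1.96) = 89%.

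**Step 4: power at 20 vs 20, share f in both extreme groups, over the ranges of q and c above.**

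| f (average graft cultures per 20) | difference | exact chi-square | unpooled normal |
|---|---|---|---|
| 0 (0) | 50 points | 90% | 95% |
| 5% (1) | 47.5 points | 86–87% | 93% |
| 10% (2) | 45 points | 82% | 89% |
| 20% (4) | 40 points | 71–72% | 79% |
| 25% (5) | 37.5 points | 65–67% | 73% |

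**Step 5: graft cultures in one extreme group only** (c = 0.5, exact chi-square, same range of q). At f = 10%, power is 87–89% if they are in CC and 83–87% if in GG. At f = 25% it is 80–88% and 70–80%.

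**The case against.** The strongest reply is that the problem may never arise.

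- **Use of graft biopsies.** Section 3.2 only makes these patients eligible. Section 4.1, which describes collection, names organoids from cholecystectomy and suspected NASH and does not list graft biopsies as a culture source. However, sections 4.2 and 4.3 culture biopsy fragments without distinction, and nothing excludes this source.
- **Native liver.** Tissue "taken from the whole liver post-transplant" can naturally be read as the recipient's removed liver, for which blood and tissue agree. This stands for section 4.1. It does not cover the separate item in section 3.2, which is a biopsy, healthy and taken after transplant.
- **Other DNA.** Section 3.2 separately requires an available DNA sample without naming its source. That is not a plan to type the graft, and the only stated method uses blood.
- **Wrong person is not always wrong group.** This is true, and Step 2 allows for it: at q = 0.106, 80% of graft cultures labelled CC are CC.
- **Size.** Neither f nor q is given, and f may be zero. With one or two graft cultures per group, power stays above 80% on both methods. This stands: a large loss needs a larger graft share, although the protocol sets no limit on it.

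The gap between 95% and 90% at f = 0 reflects the choice of method and is not part of this point.

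**Conclusion.** The point holds. Followed as written, sections 3.2, 4.1, 4.2 and 4.6 together assign graft-derived cultures the recipient's genotype, which is the wrong exposure for primary endpoint 2. This is a laboratory procedure that the protocol fixes, not a detail left to an analysis plan.

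The size is conditional. The GG vs CC difference is multiplied by (1 − f) when the graft share f is the same in both groups, and the estimate is diluted even where the test stays significant. The power figures rest on unrelated donors, Hardy-Weinberg proportions and the assumed q, c and f. With f = 0 the planned comparison is unaffected. It should be fixed, because the error cannot be found later unless tissue or culture DNA is typed.

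**What to change.** - **Section 4.6:** for every post-transplant graft sample, determine rs738409 and the other analysed variants on DNA from the tissue or its cultures, and assign the group from that result. Alternatively, state that graft-derived cultures stay out of all genotype comparisons.
- **Section 4.1:** say whether the post-transplant whole liver is the graft or the recipient's own removed liver.
- **Unchanged:** blood genotyping can stay for resections, suspected-NASH biopsies, cholecystectomies and native explanted livers.

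The cost is one more TaqMan assay for rs738409 per graft sample, plus one for each other variant analysed, on material already in hand, and one clarifying sentence. No extra patients or procedures are needed. Excluding graft cultures saves the assays but means that the 20 cultures per group must come from the other sources.
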